5.6 Investigational Product Quality Complaints

Investigators are required to report investigational product quality complaints to Tenax. This includes any instances wherein the quality or performance of a Tenax product does not meet expectations (e.g., inadequate, or faulty closure, product contamination, etc.).

5.7 Drug Accountability

Accurate records of all investigational product dispensed, used, returned, and/or destroyed must be maintained as detailed further in this section.

Investigational product will be administered only to subjects included in this study following the procedures set out in the study protocol. All dispensing will be documented.

No investigational product stock or returned inventory from a Tenax sponsored study may be removed without prior knowledge and consent by the Sponsor. If such transfer is authorized, all applicable local, state, and national laws must be adhered to for the transfer.

Tenax or its representatives must be permitted access to review the supplies storage and distribution procedures and records.

With the written agreement of Tenax, at the end of the study all unused stock, subject returned investigational product, and empty/used investigational product packaging may be destroyed at the site or a local facility. In this case, destruction records identifying what was destroyed, when and how must be obtained with copies provided to Tenax. Destruction of investigational products must be in accordance with local, state, and national laws.

5.8 Subject Compliance

Compliance will be monitored throughout the transition period (IV to oral levosimendan) and ongoing throughout the remainder of the study.

6. STUDY PROCEDURES (IV LEVOSIMENDAN)

6.1 Ongoing Weekly Infusions

Weekly visits, occurring approximately every 7 days, should be performed within ± 48 hours of the scheduled visit.

6.2 Weeks 3, 6, 12, 24, 48, and yearly, and Follow-Up Visit (at termination) (Office Visits)

Visits at Weeks 48, yearly, and Follow-Up Visit (at termination) should be performed within ± 72 hours of the scheduled weekly visit. These visits will be performed at the investigator's office. The Follow-Up Visit (at termination) will be calculated as the earlier of two years from the subject's date of entry into the TNX-LVO-05 Study or as soon as possible after study discontinuation, but within 1 week.

During this visit, the following procedures will be performed:

- Vital signs
- Body Weight (Week 3 only)

- 6MWT
- Quality of Life (QOL) assessment
- NYHA Functional Class
- Physician Assessment
- Assess adverse events
- Concomitant medications and/or procedures

For subjects who discontinue the study early, the same procedures as listed above should be performed.

Adverse events experienced by the patient since the previous visit, should be assessed at any unscheduled visit at the investigator's office.

6.3 Study Evaluations and Procedures

Study procedures will occur according to the [Time and Events Schedule](#).

Patients should be instructed to report adverse events associated with their in-home administration of the drug and any concerns that are identified between administration. Each report should be evaluated with respect to the need for an office visit for further assessment of safety.

Any adverse event identified by the patient during unscheduled visits should be recorded and followed, as appropriate, in accordance with Section 7.

6.4

7. STUDY PROCEDURES (IV TO ORAL TRANSITION)

The [Time and Events Schedule](#) summarizes the frequency and timing of efficacy, safety, or other measurements.

[Section 6.1](#) describes the transition of patients from IV to oral levosimendan. [Section 6.2](#) outlines the routine visits that will occur according to the original date the patient entered the TNX-LVO-05 study from the parent study.

During both the transition period (6.1), ongoing visits (6.2), and throughout the duration of the trial, adverse events must be collected according to Good Clinical Practice (GCP). Sites should query the patients for any new adverse events, worsening of adverse events, and changes to or new concomitant medication and/or procedures. The ongoing documentation of blood pressure and heart rate should be maintained in the patient's chart and in the case report form, as applicable.

Attention should be paid to certain safety events and changes in concomitant medications. During ongoing and routine visits, the patient should be asked if they have experienced any of the following changes:

- Palpitations associated with:
 - Shortness of breath
 - Significant lightheadedness
 - Passing out/syncope
- Edema (swelling):
 - Frequency (never, occasionally, constantly)
- Shortness of breath with activity:
 - Frequency (rarely, often, constantly)
- Diuretic use:
 - Changes (increase, no change, decrease)
- Hospitalization or Emergency Room visits

7.1 Treatment Transition: Weekly Intravenous to Daily Oral Levosimendan

All ongoing patients will be transitioned from IV to oral levosimendan over 6 weeks.

Any visit that occurs during the transition period that falls on the same day as a regularly scheduled visit (i.e. Week 3, 6, 12, 24, 48 or yearly) should include all the required procedures for both visits.

The first patient visit will occur 7-9 days following the completion of their last levosimendan infusion. Prior to starting any procedures related to the transitions, patients must sign an updated informed consent form.

Due to the ongoing pandemic (as of the date of this protocol) visits according to the [Time and Events Schedule](#) may be modified to accommodate patient scheduling. For example, a visit at transition Week 6 may be extended two additional weeks to accommodate either patient travel or hospital restrictions limiting patient visits.

Following successful transition to oral levosimendan, the port-a-cath should be removed for purposes of this study. During the transition (Weeks 0 to 6 or 8), the port-a-cath should be

maintained by the patient (i.e., flushing) according to the investigational site's institutional practices.

7.1.1 IV-Oral Transition Week 0

During this visit, the following procedures will be performed:

- Vital signs and ECG
- Physical Exam (including body weight)
- 6MWT
- Hematology and chemistry blood samples
- Pharmacokinetic sample
 - The sample should be taken before the patient consumes their first dose of oral levosimendan
- NYHA Functional Class
- Assess adverse events.
- Concomitant medications and/or procedures
- Kansas City Cardiomyopathy Questionnaire (KCCQ)
- Oral levosimendan

7.1.2 IV-Oral Transition Week 2

During this visit, the following procedures will be performed (this visit may be performed virtually, at the investigator's discretion):

- Vital signs
- Assess adverse events

7.1.3 IV-Oral Transition Week 4

During this visit, the following procedures will be performed (this visit may be performed virtually, at the investigator's discretion):

- Vital signs
- Assess adverse events
- Pharmacokinetic sample
 - *Note: if this visit is performed remotely and a home health nurse is unavailable to draw the PK sample, this sample may be missed*

7.1.4 IV-Oral Transition Week 6 – Final Visit

During this visit, the following procedures will be performed:

- Vital signs and ECG
- Physical Exam
- Hematology and chemistry blood samples
- Assess adverse events
- Pharmacokinetic sample
- 6MWT
- NYHA Functional Class
- Kansas City Cardiomyopathy Questionnaire (KCCQ)

Once a patient transitions to oral levosimendan, all references in this protocol to the administration of IV levosimendan, will no longer apply for that patient. All study drug and ancillary supplies related to the administration of IV levosimendan will be returned to the central pharmacy for destruction.

7.1.5 IV-Oral Transition Week 8

This visit is only required for patients who titrated (up or down) at the Week 6 visit.

During this visit, the following procedures will be performed:

- Vital signs
- Physical Exam
- Hematology and chemistry blood samples
- Assess adverse events
- Pharmacokinetic sample
- 6MWT
- NYHA Functional Class
- Kansas City Cardiomyopathy Questionnaire (KCCQ)

The Physical Exam, 6MWT, NYHA Functional Class, and KCCQ do not need to be performed for patients who are scheduled for a Week 8 visit, due to either up or down titration of study drug.

Following the Final Evaluation (either Week 6 or Week 8), patients will continue to visit the investigational site at weeks 3, 6, 12, 24, 48, and yearly through the Follow-Up Visit (at termination) and/or Termination visit. These visit windows will be based on the date the patient originally enrolled in the TNX-LVO-05 study. Visits that overlap may be combined into one visit.

Patients unable to return at the scheduled Week 6 or 8 visit, may have their final visit extended.

7.2 Weeks 3, 6, 12, 24, 48, and yearly through the Follow-up and/or Termination

visit (Office Visits)

Visits at Weeks 3, 6, 12, 24, 48, and yearly through the Follow-up and/or Termination visit should be performed within ± 72 hours of the scheduled weekly visit. These visits may be performed at the investigator's office. For any patients who remain on IV levosimendan, the Follow-Up Visit (at termination) will be calculated as the earlier of two years from the subject's date of entry into the TNX-LVO-05 Study or as soon as possible after study discontinuation, but within 1 week.

During this visit, the following procedures will be performed:

- Vital signs
- Physical Exam
- Hematology and chemistry blood samples
- Body Weight
- 6MWT
- Kansas City Cardiomyopathy Questionnaire (KCCQ)
- NYHA Functional Class
- Physician Assessment
- Assess adverse events
- Concomitant medications and/or procedures

If the Week 48 or yearly visit falls within two weeks of any of the IV to oral transition visits (i.e., Week 0, 2, 4, 6 or 8), these visits may be combined.

For subjects who discontinue the study early, the same procedures as listed above should be performed.

Adverse events experienced by the patient since the previous visit, should be assessed at any unscheduled visit at the investigator's office.

7.3 Pharmacokinetic Collection and Analyses

To better understand the plasma levels of levosimendan and its active metabolites, OR-1855 and OR-1896, a pharmacokinetic (PK) blood sample will be drawn at IV to Oral Transition according to the [Time and Events Schedule](#).

Pharmacokinetic samples will be collected for ongoing patients, as of the date of implementation (e.g., IRB approval) of Version 4.1 at investigational sites. Patients who discontinue the study prior to the ability to either consent or physically visit the investigational site will not be required to have a PK sample collected.

7.4 Non-successful transition to oral levosimendan

Patients who do not successfully transition to oral levosimendan may re-start IV levosimendan, within a minimum of 7 days from their last dose of oral levosimendan. Once a patient re-starts IV levosimendan, they will continue to receive study drug based on the original date of entry into the TNX-LVO-05 study (i.e., final visit in the parent study, TNX-LVO-04) return to their weekly IV levosimendan dose regimen they were on prior to starting the oral transition.

Patients that re-start IV levosimendan will not have the opportunity to be given oral levosimendan in the future.

The starting dose of IV levosimendan should be at the same rate the patient was receiving prior to the transition to oral levosimendan. After re-starting IV levosimendan, the patient should be contacted by telephone after 2 weeks to assess for any safety events.

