1.3.8 Target Plasma Concentrations of OR-1896 in chronic treatment of PH-HFpEF Patients

Levosimendan represents an active prodrug to the active metabolite OR-1896 with extended pharmacodynamic effects that parallel those of levosimendan. The elimination half-life of levosimendan itself is short (approximately 1 hour), whereas that of the metabolite OR-1896 is long (70-80 hours in heart failure subjects). During a long-term oral dosing of levosimendan with constant daily dose, the OR-1896 plasma levels achieve a steady-state with minimal daily variation.

The chronically active moiety of levosimendan administration is the metabolite OR-1896. Levosimendan is cleared within 5 hours of ending an infusion.

The wide range of OR-1896 concentrations observed in daily oral levosimendan dosing (PERSIST study, see Section 1.3.4) and weekly IV administration (HELP Study, Section 1.3.5) precludes the identification of a specific oral dose to be used in the IV to oral transition. Importantly, the range of OR-1896 plasma concentrations observed in the PERSIST study of class IIIb-IV CHF patients overlap those observed in the HELP Study of PH-HFpEF patients (Figure 3).

[figure not shown]

Figure 3. Comparison of OR-1896 Plasma Concentrations in PERSIST Study of Daily Oral Levosimendan (1mg QD, 1 mg BID) versus the HELP Study of Weekly IV Levosimendan (0.1 ug/kg/min for 24 hrs).

However, only one third of the HELP Study patients were sampled at peak OR-1896 levels, 2-3 days following their previous levosimendan IV dose. The remaining patients were sampled beyond the period of peak OR-1896 concentrations observed in a weekly IV levosimendan regimen. An opportunity to titrate patients to 4 mg total daily dose (1mg QID), as tolerated based on blood pressure and heart rate, will ensure all transitioning patients will achieve adequate steady state levels of OR-1896.

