14.3 ATTACHMENT 3: Cardiac Event Recommendations and Management

Changes in BP or HR that could represent a significant safety concern should be reported to the treating physician.

If the subject meets any of the dose-limiting event criteria, the following actions on study drug should be undertaken:

1. Blood pressure (systolic) management
 - a. Minimum allowed BP 100 mmHg systolic
 - i. If <120 on antihypertensive meds, recommend reduce or discontinue
 - ii. If >120 on antihypertensive meds, no change.
2. Low blood pressure (systolic <100) management **without symptoms**
 - a. On diuretics
 - i. With edema = no change
 - ii. No edema = reduce or withdraw
 - b. On antihypertensive meds
 - i. Reduce/withdraw
 - c. On no diuretics or antihypertensive meds
 - i. No symptoms = observe
 - ii. BP <90 = reduce levosimendan dose
3. **Symptomatic** low BP management
 - a. Follow recommendations of asymptomatic scenario (above), **and**
 - i. BP <100 mild symptoms = levosimendan dose reduction
 - ii. BP <100 severe symptoms = IV phenylephrine and levosimendan dose reduction
 - iii. BP <90 on lowest dose = discontinue study
4. Sinus tachycardia at rest
 - a. HR >110 = repeat three times per protocol and obtain BP to validate
 - b. HR >110 without symptoms = in the absence of hypotension (above), observe
 - c. HR >110 with symptoms of worsening dyspnea in the absence of hypotension (above) = levosimendan dose reduction
 - d. HR >120 (validated) without symptoms = obtain ECG to determine if sinus tachycardia or atrial-fibrillation. *(If HR > 120, the treating physician should be contacted.)*
 - i. If sinus tachycardia = levosimendan dose reduction or withdraw
 - ii. If atrial fibrillation = heart rate drug management
 - e. Persistent HR >120 despite any/all above measures = discontinue study

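### Protocol Section 7.4 allows IV restart after any failed oral transition without reference to Attachment 3, which takes some of the same patients off study, and its restart interval mixes an upper and a lower limit

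*Protocol*

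**What the plan says.** **Restart rule.** Protocol Section 7.4 opens: "Patients who do not successfully transition to oral levosimendan may re-start IV levosimendan". On timing, it says that they "may re-start IV levosimendan, within a minimum of 7 days from their last dose of oral levosimendan". On the rate it says: "The starting dose of IV levosimendan should be at the same rate the patient was receiving prior to the transition to oral levosimendan". After restart, "the patient should be contacted by telephone after 2 weeks to assess for any safety events". The section does not define an unsuccessful transition, does not separate reasons for failure, and does not cite Attachment 3.

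**Stopping rule.** Section 5.5.3 makes Attachment 3 the source of dose-limiting cardiac events and instructions for oral dosing. Attachment 3 introduces its list with "If the subject meets any of the dose-limiting event criteria, the following actions on study drug should be undertaken". Two branches end participation. Under symptomatic low pressure: "BP <90 on lowest dose = discontinue study". Under tachycardia: "Persistent HR >120 despite any/all above measures = discontinue study".

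**Other relevant text.** For Attachment 3 safety concerns during oral titration, Section 2.5 provides for down-titration or discontinuation at the physician's discretion and does not mention a return to IV. For the switch in the other direction, from IV to oral, the Time and Events Schedule footnotes and Section 7.1 give a plain window of 7-9 days.

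**The concern.** There are two separate problems.

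First, the restart rule and the stopping rule cover overlapping patients, and neither refers to the other. A patient who reaches an Attachment 3 stopping criterion while being moved to oral drug has also, on an ordinary reading, failed the transition. One passage takes that patient off study; the other makes the patient eligible to resume IV study drug.

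Second, the interval before restart is worded so that 7 days can be the latest or the earliest permitted time.

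The primary objective is safety and tolerability in extended use. The SAP reports disposition with reasons for early discontinuation (Section 3.3.1), and TEAEs leading to discontinuation of study drug and of the study (Section 3.5.1). How an affected patient enters those summaries would depend on which passage the site followed. The question also concerns re-exposure to the same drug after a possible stopping event, so it should not rest on unclear wording.

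**Working it through.** The plan has no figure of its own to reproduce here: there is no hypothesis test (SAP Section 3.1.5) and no calculated sample size (SAP Section 2.2.4). The check is a comparison of texts, with one calculation to see whether the two interval readings differ in practice.

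**1. The overlap**

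| | Section 7.4 | Attachment 3 |
|---|---|---|
| Who | All patients with an unsuccessful transition | Symptomatic systolic pressure below 90 on the lowest dose; heart rate persistently above 120 |
| Result | IV restart permitted at the pre-transition rate | Discontinue study |
| Refers to the other | No | No |

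Take a patient on 1 mg once daily with symptomatic systolic pressure of 85 mmHg. I read the lowest dose here as 1 mg daily, the starting dose in Section 5.5.1; Attachment 3 does not define it. This patient meets the Attachment 3 criterion and has not transitioned successfully, so both passages apply.

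The heading in Attachment 3 speaks of actions on study drug, while the entry speaks of the study. Either way the overlap remains, because IV levosimendan is also study drug (Section 5.4).

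The pre-transition rate may be 0.05, 0.075 or 0.1 µg/kg/min (Sections 2.5 and 5.4.1, Attachment 4). Section 7.4 states no reduction on restart.

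**2. The interval**

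Input: "whereas that of the metabolite OR-1896 is long (70-80 hours in heart failure subjects" (Section 1.3.8).

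Assumption: first-order decay from the last oral dose, ignoring metabolite formed after it.

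Formula: residual fraction = 2^(−t / half-life).

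| Time since last capsule | Half-life 70 h | Half-life 80 h |
|---|---|---|
| Day 1 (24 h) | 2^(−24/70) = 78.8% | 2^(−24/80) = 81.2% |
| Day 3 (72 h) | 49.0% | 53.6% |
| Day 7 (168 h) | 2^(−168/70) = 18.9% | 2^(−168/80) = 23.3% |
| Day 9 (216 h) | 11.8% | 15.4% |

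- If 7 days is the latest time, restart could occur with anything from about 19% to nearly 100% of the metabolite remaining.
- If 7 days is the earliest time, restart would occur with about 23% or less.
- The ratio of day 1 to day 7 is 78.8/18.9 = 4.2 at 70 h and 81.2/23.3 = 3.5 at 80 h.

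**3. How many patients**

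The documents give no transition failure rate, so the number affected cannot be calculated. For scale only: the HELP study (TNX-LVO-04) randomized 37 patients (Section 1.3.5), and entry here requires completed double-blind therapy. If HELP is the only parent study, at most 37 patients could enter, and one patient coded differently moves a whole-study percentage by at least 1/37 = 2.7 points.

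**The case against.** The strongest reply is that a site can obey both texts. Restart is optional, whereas Attachment 3 is the specific safety rule; a patient already taken off study is no longer a candidate for an option. Section 3.4 also asks that withdrawal from product be discussed, where possible, with the Medical Monitor or Sponsor. This stands in part. A reader might infer two mandatory and opposite orders, and the documents do not support that. What remains is that no text sets the order of precedence.

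Other inferences should also be set aside:

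- **Restart at full rate.** Section 7.4 says the pre-transition rate, which may already be a reduced one.
- **The telephone call as the only safeguard.** It is the only check specific to restart. A restarted patient returns to the weekly IV regimen, so the IV visits, adverse event reporting and rate-reduction provisions (Sections 5.4.1, 5.4.2, 6.1 and 6.3, Attachment 4) apply again.
- **Blood pressure and heart rate as the likeliest causes of failure.** Nothing in the documents says so. In the oral studies in cardiac patients, headache (13.3%) and cardiac failure (12.0%) were reported more often than hypotension (6.0%) (Section 1.3.6).
- **An unusable interval.** The 7-9 day window for the opposite switch makes an earliest-time reading the more plausible one. Section 7.4 still does not state it.
- **Excess risk from early restart.** Applying the fractions to the PERSIST mean of 2.7 ng/mL at 1 mg once daily (Section 1.3.8.2) gives about 2.1-2.2 ng/mL at day 1 and 0.5-0.6 ng/mL at day 7. Both lie within the 0.347-23.8 ng/mL seen on weekly IV in HELP (Section 1.3.8.1).
- **An invalid comparison between sites.** None is planned (SAP Section 3.1.6). The issue is consistent coding of a few patients in the pooled tables.

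Finally, SAP Section 4 cites protocol version 5.0, while the protocol available is version 4.1. Whether Section 7.4 changed in between cannot be determined from these documents.

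**Conclusion.** The point holds in limited form, as a should-fix. Read literally, Section 7.4 admits to IV restart some patients whom Attachment 3 takes off study, and no text says which passage governs. The overlap is confined to the two Attachment 3 criteria, and its size is unknown.

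Separately, the restart interval contains both an upper and a lower limit. The two readings differ by about 3.5- to 4.2-fold in residual OR-1896 when day 1 is compared with day 7. That figure rests on the protocol's 70-80 h half-life and simple first-order decay, and it describes a residual fraction, not a demonstrated hazard.

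This is more than missing detail, because a stated re-exposure rule cannot be applied uniformly as written and it bears on the primary objective. No position is taken on which clinical rule, interval or rate is right.

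**What to change.** 1. Reconcile Sections 2.5, 5.5.3 and 7.4 and Attachment 3, so that all agree on whether a patient who met a study-discontinuation criterion on oral drug may restart IV. Which way they agree is for the sponsor to decide.
2. Replace the interval wording in Section 7.4 with one unambiguous bound, as the sponsor intends.
3. Use the eCRF entries already required for the reason for discontinuation (Section 3.4.1) and for events of interest and dose adjustment (Section 9.1.5) to record which Attachment 3 criterion, if any, was met. Disposition and TEAEs leading to discontinuation can then be coded consistently.

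The cost is a wording amendment and a completion instruction for existing fields. It needs no extra patients, visits or assessments.
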